### 3.2 Exclusion Criteria

Any potential subject who meets any of the following criteria will be excluded from participating in the study.

1. Subject has a diagnosis of primary amyloidosis, monoclonal gammopathy of undetermined significance, or smoldering multiple myeloma. Monoclonal gammopathy of undetermined significance is defined by presence of serum M-protein  $< 3$  g/dL; absence of lytic bone lesions, anemia, hypercalcemia, and renal insufficiency related to the M-protein; and (if determined) proportion of plasma cells in the bone marrow of 10% or less. Smoldering multiple myeloma is defined as asymptomatic MM with absence of related organ or tissue impairment end organ

damage

2. Subject has a diagnosis of Waldenström's disease, or other conditions in which IgM M-protein is present in the absence of a clonal plasma cell infiltration with lytic bone lesions
3. Subject has prior or current systemic therapy or SCT for MM, with the exception of an emergency use of a short course (equivalent of dexamethasone 40 mg/day for a maximum 4 days) of corticosteroids before treatment.
4. Subject has a history of malignancy (other than MM) within 5 years before the date of enrollment (exceptions are squamous and basal cell carcinomas of the skin and carcinoma in situ of the cervix, or malignancy that in the opinion of the investigator, with concurrence with the sponsor's medical monitor, is considered cured with minimal risk of recurrence within 5 years).
5. Subject has had radiation therapy within 7 days of enrollment.
6. Subject has had plasmapheresis within 28 days of enrollment.
7. Subject is exhibiting clinical signs of meningeal involvement of MM.
8. Subject has known chronic obstructive pulmonary disease (COPD) (defined as a forced expiratory volume [FEV] in 1 second <60% of predicted normal), persistent asthma, or a history of asthma within the last 2 years (intermittent asthma is allowed). Subjects with known or suspected COPD or asthma must have a FEV1 test during screening.
9. Subject is known to be seropositive for history of human immunodeficiency virus (HIV) or known to have active hepatitis B or hepatitis C.
10. Subject has any concurrent medical or psychiatric condition or disease (eg, active systemic infection, uncontrolled diabetes, acute diffuse infiltrative pulmonary disease) that is likely to interfere with the study procedures or results, or that in the opinion of the investigator, would constitute a hazard for participating in this study.
11. Subject has clinically significant cardiac disease, including:
  - myocardial infarction within 1 year before enrollment, or an unstable or uncontrolled disease/condition related to or affecting cardiac function (eg, unstable angina, congestive heart failure, New York Heart Association Class III-IV);
  - uncontrolled cardiac arrhythmia (National Cancer Institute Common Terminology Criteria for Adverse Events [NCI CTCAE] Version 4 Grade  $\geq$ 2) or clinically significant ECG abnormalities;
  - screening 12-lead ECG showing a baseline QT interval as corrected by Fridericia's formula (QTcF) >470 msec.
  - uncontrolled hypertension
12. Subject has known allergies, hypersensitivity, or intolerance to corticosteroids, monoclonal antibodies or human proteins, or their excipients (refer to respective package inserts or IB) or known sensitivity to mammalian-derived products.
13. Subject has plasma cell leukemia (according to World Health Organization [WHO] criterion:  $\geq$ 20% of cells in the peripheral blood with an absolute plasma cell count of more than  $2 \times 10^9/L$ ) or POEMS syndrome (polyneuropathy, organomegaly, endocrinopathy, monoclonal protein, and skin changes).

14. Subject is known or suspected of not being able to comply with the study protocol (eg, because of alcoholism, drug dependency, or psychological disorder). Subject has any condition for which, in the opinion of the investigator, participation would not be in the best interest of the subject (eg, compromise the well-being) or that could prevent, limit, or confound the protocol-specified assessments.
15. Subject is a woman who is pregnant, or breast-feeding, or planning to become pregnant while enrolled in this study within 30 days after the last dose of lenalidomide or carfilzomib, or within 4 months after the last dose of isatuximab. Or, subject is a man who plans to father a child while enrolled in this study, within 4 weeks after the last dose of lenalidomide, within 90 days of the last dose of carfilzomib, or within 4 months after the last dose of isatuximab.
16. Subject has had major surgery within 2 weeks before enrollment or has not fully recovered from surgery, or has surgery planned during the time the subject is expected to participate in the study. Kyphoplasty or vertebroplasty is not considered major surgery.
17. Subject has received an investigational drug (including investigational vaccines) or used an invasive investigational medical device within 4 weeks before enrollment or is currently enrolled in an interventional investigational study.
18. Subject has contraindications to required prophylaxis for deep vein thrombosis and pulmonary embolism.
19. Incidence of gastrointestinal disease that may significantly alter the absorption of oral drugs.
20. Peripheral neuropathy  $\geq$  Grade 2 on clinical examination during the screening period.
21. Systemic treatment with strong inhibitors of CYP1A2 (fluvoxamine, enoxacin), strong inhibitors of CYP3A (clarithromycin, telithromycin, itraconazole, voriconazole, ketoconazole, nefazodone, posaconazole) or strong CYP3A inducers (rifampin, rifapentine, rifabutin, carbamazepine, phenytoin, phenobarbital), or use of Ginkgo biloba, St. John's wort within 14 days before the first dose of study treatment.

### **3.3 Inclusion of Women and Minorities**

Both men and women of all races and ethnic groups are eligible for this trial.

## **4. REGISTRATION**

### **4.1 General Guidelines for Dana-Farber/Harvard Cancer Center (DF/HCC) Institutions**

Institutions will register eligible participants in the Clinical Trials Management System (CTMS) OnCore. Registrations must occur prior to the initiation of any protocol-specific therapy or intervention. Any participant not registered to the protocol before protocol-specific therapy or intervention begins will be considered ineligible and registration will be denied.

An investigator will confirm eligibility criteria and a member of the study team will complete the protocol-specific eligibility checklist.

Following registration, participants may begin protocol-specific therapy and/or intervention. Issues that would cause treatment delays should be discussed with the Overall Principal Investigator (PI). If the subject does not receive protocol therapy following registration, the subject must be taken off-study in the CTMS (OnCore) with an appropriate date and reason entered.

#### **4.2 Registration Process for DF/HCC Institutions**

Applicable DF/HCC policy (REGIST-101) must be followed.

#### **4.3 General Guidelines for Other Investigative Sites**

Not applicable

#### **4.4 Registration Process for Other Investigative Sites**

Not applicable

### **5. TREATMENT PLAN**

#### **5.1 Treatment Regimen**

Carfilzomib, lenalidomide, dexamethasone, and isatuximab will be administered on a 28-day treatment cycle. All subjects will perform stem cell collection after 4 cycles of therapy.

For patient undergoing upfront stem cell transplant (SCT):

4 cycles of therapy followed by stem cell collection, high-dose chemotherapy, and autologous SCT followed by 2 additional cycles of therapy then maintenance.

For patients deferring SCT following collection:

4 cycles of therapy followed by stem cell collection followed by 4 additional cycles of therapy then maintenance.

Carfilzomib 56 mg/m^2 IV on Days 1, 8, 15

Lenalidomide 25 mg orally (po) on Days 1-21

Isatuximab 10 mg/kg IV Q1 week for 8 weeks, then Q2 weeks for 16 weeks, thereafter Q4 weeks

Dexamethasone 20 mg po will be administered day of and day after all doses of carfilzomib (Days 1, 2, 8, 9, 15, and 16) and isatuximab (Cycles 1 and 2 Days 22 and 23). The dexamethasone 20 mg oral or IV dose administered as a preinfusion medication on isatuximab infusion days (Days 1, 8, 15, 22) replaces the oral dexamethasone dose for that day.

\*All subjects with receive carfilzomib 20 mg/m^2 on Day 1 Cycle 1

**Maintenance:**

Patients must achieve a PR or better to continue onto maintenance therapy on the study.

28-day Maintenance Cycle until progressive disease (PD) or unacceptable toxicity. Subjects will be stratified based on cytogenetics (deletion (del) 17, translocation (t)(4:14), t(14;16), t(14;20), 1q duplication).

Standard-risk:

Lenalidomide 10 mg po Days 1-21

High-risk:

Carfilzomib 56 mg/m^2 (or last tolerated dose) IV Days 1, 15

Lenalidomide 10 mg po Days 1-21

Isatuximab 10 mg/kg IV Day 1 for up to 24 cycles of maintenance (two years), then discontinue

In the maintenance phase, dexamethasone, 20 mg orally or IV will be administered to subjects as a preinfusion medication prior to isatuximab dosing. When dexamethasone is reduced to 20 mg/week and is given as preinfusion medication, subjects may receive low-dose methylprednisolone ( $\leq 20$  mg) orally (or equivalent in accordance with local standards) for the prevention of delayed infusion-associated reactions (IARs), as clinically indicated.

Because lenalidomide is primarily excreted unchanged by the kidney, adjustments to the starting dose of lenalidomide are recommended to provide appropriate drug exposure in patients with renal impairment. Lenalidomide dose adjustment should be instituted for patients with a CrCl  $\leq 50$  mL/min. The recommended doses for patients with multiple myeloma and renal impairment are shown below in Table 9. If during treatment a patient's renal status changes, the dose should be adjusted as shown in Table 9. Similarly, adjustments to the starting and ongoing dosing of carfilzomib are recommended in the setting of hepatic impairment. The doses should be adjusted as shown in Table 10.

Stem cell collection and SCT should be done per institutional and FACT guidelines. The decision whether a patient will proceed to stem cell transplant will be made on the basis of treating physician recommendations and patient preference. Physician recommendations are typically based on disease response and on how well subjects are tolerating treatment. This kind of decision-making process related to stem cell transplant is considered standard of care in the multiple myeloma field. Subjects who do not proceed to stem cell transplant may receive a total of 8 cycles of therapy followed by maintenance. Those patients proceeding with stem cell transplant will receive an additional 2 cycles of therapy post-SCT followed by maintenance. Prior to continuing induction therapy, all stem cell harvest-related toxicity or stem cell

transplant-related toxicity must be improved such the patient meets criteria to treat outlined in section 5.2 of the protocol.

## 5.2 Pre-Treatment Criteria

A new cycle of treatment may begin on the scheduled Day 1 of a new cycle if the following criteria are met within 24 hours of Day 1:

- ANC  $\geq 1,000/\text{mm}^3$  (growth factor support is permitted during cycles with the exception of Cycle 1 Day 1 (C1D1); it is allowed on the same day as treatment administration).
- Platelet count  $\geq 50,000/\text{mm}^3$  (platelet support is permitted during cycles of treatment; it is allowed on the same day as treatment administration, including C1D1).
- Any lenalidomide-related allergic reaction/hypersensitivity or sinus bradycardia/other cardiac arrhythmia AE that may have occurred has resolved to < Grade 1.
- Any other lenalidomide, carfilzomib, or isatuximab-related adverse event that may have occurred has resolved to <Grade 2.
- Herpes zoster lesions, if present, are dry.

If these conditions are not met on Day 1 of a new cycle, the subject will be evaluated weekly and a new cycle of therapy will not be initiated until the toxicity has resolved as described above. The maximum amount of time that treatment may be held for these toxicities to resolve is 3 weeks. If drug is held for more than 3 weeks due to toxicity, the patient is to discontinue all study treatment and enter the survival follow-up phase of the study.

For intra-cycle dosing on days where laboratory studies are scheduled, the following criteria must be met:

- Platelet count  $\geq 30,000$  (platelet transfusion support is permitted to meet criteria)
- Absolute neutrophil  $\geq 500/\text{mm}^3$  (growth factor support is permitted during cycles with the exception of Cycle 1 Day 1 (C1D1); it is allowed on the same day as treatment administration).

Intra-cycle dose modifications for all drugs will be allowed based on toxicity and according to dose modifications outline in Section 6.1, Table 9.

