## **5.6 Duration of Follow Up**

Participants will be followed every three months after removal from protocol therapy for 2 years or until confirmation of progressive disease, initiation of subsequent myeloma therapy, death, withdrawal of consent, or loss of follow up, whichever occurs first. Participants removed from protocol therapy for unacceptable adverse event(s) will be followed until resolution or stabilization of the adverse event and then every three months until PD or initiating subsequent therapy.

The first follow up visit should occur three months after the end of treatment visit.

Following disease progression or initiation of subsequent myeloma therapy, participants may be followed-up for survival by telephone contact every three months or chart review for a period of five years from study enrollment.

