## **5.7 Criteria for Taking a Participant Off Study**

Participants will be removed from study when any of the following criteria apply:

- Lost to follow-up
- Withdrawal of consent for data submission
- Death

The reason for taking a participant off study, and the date the participant was removed, must be documented in the CRF. In addition, the study team will ensure Off Treatment/Off Study information is updated in OnCore in accordance with DF/HCC policy REGIST-101.

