Hyperthyroidism or hypothyroidism	Omit lenalidomide for remainder of cycle, evaluate, and initiate appropriate therapy. Restart lenalidomide next cycle at 1 dose decrement	No adjustment required
Congestive heart failure (CHF)	Any subject with symptoms of CHF, whether or not lenalidomide related, must have the dose held until resolution or return to baseline. If CHF was felt to be lenalidomide related, reinstate by one dose decrement after return to baseline. If no resolution of CHF after 2 weeks, the subject will be withdrawn from the study.	Any subject with symptoms of CHF, whether or not carfilzomib related, must have the dose held until resolution or return to baseline. If CHF was felt to be carfilzomib related, reinstate by one dose decrement after return to baseline. If no resolution of CHF after 2 weeks, the subject will be withdrawn from the study.
Hypertension including Hypertensive Crises	NA	≥ Grade 3: Carfilzomib attribution, hold drug until resolved to ≤ Grade 2. Resume at one level dose reduction
Toxicity	Recommended Action	
	Lenalidomide	Carfilzomib

Heart problems, including rapid, strong, or irregular heartbeat
 
Heart attack, reduced blood flow to the heart, abnormal amount of fluid between the heart and lining around the heart, and swelling/irritation of the lining around the heart
	
NA
	
≥ Grade 3: Carfilzomib attribution, hold drug until resolved to ≤ Grade 1. Resume at one level dose reduction

Pericardial Effusion
	
NA
	
≥ Grade 3: Carfilzomib attribution, hold drug until resolved to Grade 1. Resume at one level dose reduction

Pericarditis
	
NA
	
≥ Grade 3: Carfilzomib attribution, hold drug until resolved to Grade 1. Resume at one level dose reduction

Toxicity
	
Recommended Action
	
	
Lenalidomide
	
Carfilzomib

Pulmonary Hypertension
	
NA
	
= Grade 2: Carfilzomib attribution, Reduce drug: one level dose reduction
 
≥ Grade 3: Carfilzomib attribution, hold drug until resolved to ≤Grade 2. Resume at one level dose reduction

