Secondary Analysis: Secondary analyses will evaluate overall response rate, MRD rate, PFS and OS. Overall response rate will be percent of patients who achieve at least partial response (PR). Percent of patients achieving MR or better will also be collected as clinical benefit response. MRD rate after 4 cycles, at completion of induction, and at 24 months will be determined by deep sequencing of genomic deoxyribonucleic acid from bone marrow samples using rearranged Ig locus-specific primers (Adaptive, Seattle, WA). PFS will be defined as the time from first dose of study treatment to the first documentation of PD or death from any cause during study. OS will be defined as the time from first dose of study treatment to death from any cause. For responders, time to response (TTR) and duration of response (DOR) will be analyzed. TTR will be defined as the time from first dose of study treatment to the first documentation of response (either PR, very good partial response (VGPR) or CR, nCR, and sCR). DOR will be defined as the time from the first PR, VGPR, or CR to the first documentation of PD or death, whichever occurs earlier.

Response rates together with confidence intervals (CIs) will be provided. Kaplan-Meier curves will be used to characterize the time-to-event outcomes (PFS, OS, response duration) when there is censoring; univariate summary statistics will be provided for TTR. In addition, outcomes including median PFS and median OS will be calculated within sub-groups based on risk status (standard vs high) and MRD status (positive vs negative).

A 90% CI for the response rate will be constructed for evaluating the efficacy of KRDI. Kaplan-Meier curves will be constructed to characterize PFS, OS, and DOR. One sample standard inferences for PFS, OS, and DOR will be made accordingly.

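### Section 5.2 and the heart-failure row of Table 9 end follow-up because of toxicity, in conflict with Sections 5.6 and 5.7 and Table 14

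*Combined protocol and SAP*

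**What the plan says.** Four places govern what happens to a patient who stops treatment for toxicity.

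- **Section 5.2.** If drug is held for more than 3 weeks because of toxicity, the patient stops every study drug and is to "enter the survival follow-up phase of the study".
- **Section 6.1, Table 9, congestive heart failure row (lenalidomide and carfilzomib columns).** "If no resolution of CHF after 2 weeks, the subject will be withdrawn from the study".
- **Section 5.6.** A participant taken off protocol therapy because of toxicity judged unacceptable "will be followed until resolution or stabilization of the adverse event and then every three months until PD or initiating subsequent therapy". Survival-only contact has its own, later trigger: "Following disease progression or initiation of subsequent myeloma therapy, participants may be followed-up for survival by telephone contact every three months or chart review".
- **Section 5.7.** "Participants will be removed from study when any of the following criteria apply": three reasons follow, namely loss to follow-up, withdrawal of consent for data submission, and death.

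The follow-up column of Tables 14A and 14B, every 12 ± 3 weeks, includes physical examination, SPEP, IFE and free light chains. Section 12.1 defines PFS as the "time from first dose of study treatment to the first documentation of PD or death from any cause during study" and analyses PFS, OS and DOR by Kaplan-Meier.

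**The concern.** The same patient is given two follow-up paths. Under 5.2, disease assessment ends when treatment ends; under 5.6 and Table 14 it continues until progression or the next therapy. Under Table 9, a patient whose cardiac event is unresolved leaves the study, although 5.6 asks for follow-up until the event resolves or stabilizes and 5.7 has no such off-study reason.

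Safety, PFS and OS are secondary objectives, and DOR is among the secondary analyses. A PFS event must be documented, and documented during study. A site that applies 5.2 or the Table 9 row as written therefore creates censoring caused by toxicity. If patients who stop for toxicity go on to do worse than those who continue, that censoring is informative and Kaplan-Meier reads too high. Section 12 gives no censoring rule for these patients.

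**Working it through.** **1. The plan's own figures.** The plan gives no number on this point. Its one design calculation (Section 12.1) reproduces from the exact binomial tail, with reference rate 0.27 and alternative 0.43:

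- n = 50, reject at 19 or more CRs: P(X ≥ 19 | 0.27) = 0.059; P(X ≥ 19 | 0.43) = 0.804.
- n = 45, reject at 17 or more CRs: P(X ≥ 17 | 0.27) = 0.075; P(X ≥ 17 | 0.43) = 0.804.

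This test does not use PFS, DOR or OS, so nothing below alters it.

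**2. The passages side by side.**

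| Question | 5.2 (hold over 3 weeks) | Table 9 (unresolved heart failure) | 5.6, 5.7 and Table 14 |
|---|---|---|---|
| On study after stopping? | Yes | No | Yes, unless lost, consent withdrawn, or dead |
| Scheduled disease assessment? | None stated | None | Every three months until progression or next therapy |
| Survival follow-up? | Yes, at once | None | Yes, after progression or next therapy |
| Event followed to resolution or stabilization? | Not stated | Not after withdrawal | Yes |

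**3. What is lost on a literal reading.** Under 5.2, the loss is scheduled progression assessment between stopping treatment and the earlier of progression or next therapy. Deaths and OS are still captured. Under the heart-failure row, survival follow-up and scheduled follow-up of the event are lost as well.

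**4. Possible size. All inputs are assumed; none comes from the documents.** Let f be the fraction stopped and censored early, S_c the PFS of those who continue and S_s the PFS of those who stop.

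- True PFS = (1 − f)·S_c + f·S_s. Kaplan-Meier reads about S_c, so the overstatement is about f·(S_c − S_s).
- With S_c = 0.80 and S_s = 0.60 at 24 months and f = 0.10: 0.9 × 0.80 + 0.1 × 0.60 = 0.78, an overstatement of 2 points.
- With f = 0.20: 0.8 × 0.80 + 0.2 × 0.60 = 0.76, an overstatement of 4 points.
- For scale, the standard error of an 80% estimate from 50 uncensored patients is √(0.80 × 0.20 / 50) = 0.057, or 5.7 points.

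A simulation with other assumptions (median PFS 60 months, stops spread evenly over months 1 to 12, progression hazard 1.5 to 3 times higher after the stop, censoring at the stop) overstates 36-month PFS by 0.5 to 1.6 points with 5% affected, 1.0 to 3.3 with 10%, and 2.1 to 6.5 with 20%. If the later hazard is unchanged, only precision is lost.

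Both illustrations treat every event after the stop as unseen. That is not what 5.2 implies for deaths, so they indicate scale and are not estimates.

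**The case against.** The strongest reply is that the conflict may not bite.

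- The survival follow-up phase named in 5.2 is not a defined term, and Table 14 has a single follow-up column that includes the myeloma tests. A site working from the calendar would keep assessing disease. Withdrawal from the study in Table 9 may have been meant as coming off treatment.
- Section 5.2 is not the only text on long holds. The isatuximab, carfilzomib/lenalidomide and dexamethasone parts of Section 6.1 send delays over 3 weeks to the Principal Investigator, with re-treatment at that investigator's discretion. The treatment discontinuation text speaks of leaving treatment after a delay over 21 days, with an exception by agreement. Not every long hold ends in the 5.2 exit.
- Section 5.6 itself ends disease assessment at the next therapy. A newly diagnosed patient taken off treatment early may start one soon, so the lost interval may be short. Chart review could still find some progressions.
- PFS carries no decision rule here, and 2 to 4 points is below the 5.7-point standard error.

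These points stand as limits on reach and size. They do not remove the contradiction. Undefined terms make it more likely that sites will act differently, and sampling error does not excuse a bias that a wording change prevents.

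**Conclusion.** Both contradictions are in the current text and should be reconciled: 5.2 against 5.6 and Table 14, and the Table 9 heart-failure row against 5.7 and 5.6. Read literally, the first may bias PFS and DOR; the second may also bias OS, for the heart-failure group only. The amount cannot be derived from the documents; 2 to 4 points at 24 months holds only under the assumed inputs shown.

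A reader might infer three stronger conclusions that the documents do not support:

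- **OS is lost under 5.2.** It is not; that rule sends patients into survival follow-up, and deaths remain visible.
- **The conflict causes missing response status after cycle 4.** A patient stopped before then lacks an after-4-cycles assessment under 5.6 as well, since those visits are quarterly and not tied to cycle 4. Section 12.1 already considers 10% not completing 4 cycles.
- **Cardiac outcomes are wholly lost.** Section 7.2 requires the outcome of every adverse event to be recorded. Section 7.4 collects events until 60 days after last treatment in those who withdraw from treatment. Section 7.1 requires possibly related events arising after treatment or study ends to be reported whatever the delay. What lapses is scheduled follow-up of the existing event.

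**What to change.** Leave every hold, dose and treatment-stopping rule unchanged, and reconcile the passages on follow-up only. In Section 5.2 and in both columns of the Table 9 heart-failure row, state that a patient who comes off protocol therapy for toxicity remains on study and is followed per Section 5.6: until the event resolves or stabilizes, then disease assessment every three months until progression or the start of subsequent therapy, then survival. State that Section 5.7 is the only list of off-study reasons.

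The cost is an amendment of wording. It adds no visits beyond those in Section 5.6 and Table 14. It is worth making early, because assessments missed under the present text cannot be recovered later.
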